6.6. Yale Safety Reporting and Monitoring (DSMP)

The Yale Cancer Center (YCC) Data and Safety Monitoring Committee (DSMC) will provide the primary oversight of data and safety monitoring. The Yale DSMC will review and monitor compliance, toxicity and deviations from this study. The committee is composed of clinical specialists with experience in oncology and who have no direct relationship with the study. Information that raises any questions about participant safety will be addressed with the Principal Investigator.

The DSMC will review this protocol bi-annually, at a minimum. Information to be provided to the committee includes: a study narrative by the PI, a summary DSMC report produced by OnCore (which includes participant accrual, response, trial status history, SAEs, adverse events, deviations and survival); audit results, and monitoring reports, as applicable. Other information (e.g., scans, laboratory values, etc.) will be provided upon request. Upon completing the review, the DSMC will approve whether the study should continue as planned, require modification/ amendment, or be placed on administrative hold with accrual temporarily suspended.

Trials being monitored by the YCC DSMC will remain under the YCC DSMC purview until a DSMC review has occurred that includes the research activity of the last subject who completed the intervention, or until the DSMC feels there are no patient safety concerns that require further monitoring. The DSMC will determine the length of continued DSMC review.

The DSMC has authority to intervene in the conduct of these studies as necessary to ensure the safety of the participants and to maintain the highest quality in the clinical research performed at YCC. The DSMC has the authority to require additional monitoring and/ or more frequent reporting on study progress and serious adverse events.

6.7. Pregnancies

It is the responsibility of investigators or their designees to report any pregnancy or lactation in a subject (spontaneously reported to them), including the pregnancy of a male subject's female partner that occurs during the trial or within 120 days of completing the trial.

All subjects and female partners of male subjects who become pregnant must be followed to the completion/termination of the pregnancy. Pregnancy outcomes of spontaneous abortion, missed abortion, benign hydatidiform mole, blighted ovum, fetal death, intrauterine death, miscarriage and stillbirth must be reported as serious events (Important Medical Events). If the pregnancy continues to term, the outcome (health of infant) must also be reported.

Such events must be reported within 24 hours to Yale IRB.

6.8. Warnings and Precautions

No evidence available at the time of the approval of this study protocol indicated that special warnings or precautions were appropriate, other than those noted in the provided Investigator Brochures. Additional safety information collected between IB updates will be communicated in the form of Investigator Notifications. This information will be included in the patient informed consent and should be discussed with the patient during the study as needed.

7. CORRELATIVE/SPECIAL STUDIES

Correlative studies will be conducted on serial tumor biopsy and blood specimens. All patients will undergo a tumor biopsy prior to initiation of trial therapy, and after their 5th treatment with nivolumab (study week 10). Blood will be drawn prior to each tumor biopsy to allow additional correlative studies.

Tissue from Serial Tumor Biopsies:

- a. Multiplexed quantitative immunofluorescence will be used to evaluate multiple markers on tumor/ immune cells, including, but not limited to, PD-L1, PD-1, CK, CD4, CD8, CD20, Ki67, granzyme B, and IDO1.
- b. RNA, TCR and DNA sequencing (with neoantigen analysis)
- c. Additional studies, depending on tissue availability, may include: functional T cell studies (neoantigen stimulation assay, T cell culture) and generation of patient derived xenografts.

Serial Blood Draws:

- a. Mass cytometer (CyTOF 2, DVS Sciences) will be used to comprehensively characterize phenotypic (CD45, CD3, CD8, CD4, CD33, CD11b, CD123, CD56, CD16, CD20, CD66b, CD68, TBET, GATA-3, FOXP-3, CD14, CCR7, CD45RA, $\gamma\delta$ TCR) and functional (KI-67, HLA-DR, CD25, PD-1, CD80, CD16, IFN γ , TNF α , Granzyme B, Caspase 3, PARP) changes of blood cells in relation to changes in tumor tissue.
- b. Tetramer staining using neoantigenic peptides or ELISPOT (neoantigen stimulation assay).

8. CRITERIA FOR RESPONSE

Anti-tumor activity: data on objective response, progression free survival, and duration of response will be listed for all patients in the study and summarized overall.

Objective response is defined as a complete or partial response, as determined by investigator assessment using RECIST v1.1 and irRC (see appendix 3 and 4) and confirmed by repeat assessments ≥ 4 weeks after initial documentation. Patients not meeting these criteria, including patients without any post baseline tumor assessment, will be considered non-responders in the analysis of objective response.

Duration of objective response will be analyzed for the subset of patients who achieved an objective response. Duration of response is defined as the time from the initial complete or partial response to the time of disease progression or death, whichever occurs first. If a patient does not experience death or disease progression before the end of the study, duration of response will be censored at the day of the last tumor assessment. If no tumor assessments were performed after the date of the first occurrence of a complete or partial response, duration of objective response will be censored at the date of the first occurrence of a complete or partial response plus 1 day.

Progression-free survival is defined as the time from the first day of nivolumab treatment until progression of disease using RECIST v1.1 and irRC (see appendix 3 and 4). If a patient has not experienced progressive disease or death, PFS will be censored at the day of the last tumor assessment. Patients with no post baseline tumor assessments will be censored at the date of first study treatment plus 1 day.

[figure not shown]
Overall survival is defined as the time from the first day of treatment until death from any cause. If a patient has not experienced death, OS will be censored at the day of last follow-up.

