4.3.4. Treatment Discontinuation Criteria

For all subjects, global deterioration of health status requiring discontinuation of treatment without objective evidence of disease progression at that time should be reported as 'symptomatic deterioration' in the source data. Every effort should be made to document objective progression (i.e., radiographic confirmation) even after discontinuation of treatment.

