5.2. On-Study Visits

The day of the nivolumab infusion (every 2 weeks) and the day of the ipilimumab infusion (every

6 weeks):

- 1) History and physical examination
- 2) Measurement of height, weight and vital signs (including blood pressure, heart rate, respiratory rate, oxygen saturation, and temperature).
- 3) Performance status evaluation
- 4) Review concomitant medications
- 5) Adverse events assessment
- 6) CBC with differential, serum chemistry (Na, K, Cl, CO₂, BUN, creatinine, glucose, calcium), magnesium, phosphate, liver function tests (albumin, total protein, alkaline phosphatase, total and, ALT, AST), LDH
- 7) Pregnancy test (serum or urine) for women of childbearing potential (every 6 weeks)
- 8) Administration of nivolumab and/or ipilimumab accordingly.
- 9) TSH with reflex free T4 and free T3 (every 6 weeks)

Tumor response assessment will occur every 9 weeks after initiating trial therapy for the first 24 weeks, and thereafter every 12 weeks.

Tumor biopsies (excision, core or forceps) will be performed 9 to 10 weeks after initiating trial therapy after the 4th or 5th nivolumab infusion to allow for analysis of pharmacodynamics changes related to trial therapy (see Sections 4.1.1 and 7). Blood will be drawn for correlative studies the day of the first four nivolumab infusions, and the week after the 5th nivolumab infusion.

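### Section 8 is inconsistent on whether death is a PFS event, and its rule for unscanned patients, followed as written, drops deaths before the first scan from PFS

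*Combined protocol and SAP*

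**What the plan says.** Three consecutive sentences in Section 8 govern PFS.

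- Definition: "Progression-free survival is defined as the time from the first day of nivolumab treatment until progression of disease using RECIST v1.1 and irRC". Death is not mentioned.
- General censoring: "If a patient has not experienced progressive disease or death, PFS will be censored at the day of the last tumor assessment". This makes sense only if death is an event.
- Fallback: "Patients with no post baseline tumor assessments will be censored at the date of first study treatment plus 1 day". It carries no condition on being alive.

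Two neighbouring definitions in the same section do name death. Duration of response runs "to the time of disease progression or death, whichever occurs first". For OS, "Overall survival is defined as the time from the first day of treatment until death from any cause".

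On scan timing, Section 5.2 states: "Tumor response assessment will occur every 9 weeks after initiating trial therapy for the first 24 weeks, and thereafter every 12 weeks". The Study Calendar (Section 5.4) places trial imaging at week 9, at week 18, and every 12 weeks after that. Section 9 gives no PFS rule of its own and refers back to Section 8 for the definitions.

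On irPD, Appendix 4 requires the increase in tumor burden to be confirmed at least 4 weeks after it is first documented. Neither Appendix 4 nor Section 8 says which of the two dates is the event date.

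**The concern.** A patient who dies in, say, week 5 will often have no scan after baseline. The fallback sentence then censors that patient at first treatment plus 1 day. Dosing starts on Day 1 (Section 4.3), so this is Day 2. The death date is known and the same death is an OS event, but it disappears from PFS under both RECIST v1.1 and irRC.

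This censoring is informative. It removes the earliest failures and can only raise the PFS curve. It also lets reported PFS lie above OS before week 9, which cannot happen when death is a PFS event. The affected outputs are the Kaplan-Meier estimates, the log-rank comparison and the Cox models that Section 9 plans for PFS.

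**Working it through.** **Reading the sentences together.** The definition omits death, the second sentence implies it, and the third overrides the second for anyone unscanned unless the reader supplies a condition that is not written. A programmer who follows the third sentence drops the deaths; one who follows the second keeps them.

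**Inputs.** Primary cohort n = 40 (Section 4.1). First scan at week 9, second at week 18 (Section 5.4). Assumed, because the documents give no value: k deaths at week 5 with no post-baseline scan, k = 1, 2, 4 or 6; 16 of 40 patients event-free past week 18; all other patients progress at week 9 or 18; no other early censoring.

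**Formula.** Let d = k/40, and let S0(t) be PFS among patients who do not die unscanned before week 9. With the deaths counted, S(t) = (1 − d) × S0(t) from week 9 on. As written, the k patients leave the risk set on Day 2 and the analysis reports S0(t) = S(t)/(1 − d). The inflation factor is 1/(1 − d) = 40/(40 − k).

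| k | Factor 40/(40 − k) | Week-18 PFS, deaths counted | Week-18 PFS, as written | Shift (points) | PFS just before week 9, as written | OS just before week 9 |
|---|---|---|---|---|---|---|
| 1 | 1.03 | 16/40 = 40.0% | 16/39 = 41.0% | 1.0 | 100% | 39/40 = 97.5% |
| 2 | 1.05 | 40.0% | 16/38 = 42.1% | 2.1 | 100% | 38/40 = 95.0% |
| 4 | 1.11 | 40.0% | 16/36 = 44.4% | 4.4 | 100% | 36/40 = 90.0% |
| 6 | 1.18 | 40.0% | 16/34 = 47.1% | 7.1 | 100% | 34/40 = 85.0% |

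The standard error of the 40% estimate is √(0.4 × 0.6/40) = 0.077, or 7.7 points.

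**Median.** The effect comes in steps because progressions are found at scans. Take k = 6 with 14 progressions at week 9 and 8 at week 18. With deaths counted, week-9 PFS is 20/40 = 50.0% and the median falls at week 9. As written it is 20/34 = 58.8% at week 9 and 12/34 = 35.3% at week 18, so the median moves to week 18. With k = 2 and the same progressions, week-9 PFS is 24/40 = 60.0% against 24/38 = 63.2%, and the median stays at week 18 either way.

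**Other early censoring.** If c living patients are also unscanned and properly censored on Day 2, the factor becomes (40 − c)/(40 − c − k). For c = 2 and k = 4 this is 38/34 = 1.12 instead of 1.11.

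**Is k from 1 to 6 reasonable?** Only rough context is available. Assuming exponential survival, the 69% one-year OS in Table 2.2.2 gives 40 × (1 − 0.69^(9/52)) = 2.5 deaths by week 9. The 8-month second-line median survival in Section 2.1 gives 40 × (1 − 0.5^(2.07/8)) = 6.6, taking 9 weeks as 2.07 months. Both figures count all deaths, scanned or not, and come from other populations.

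**irPD date.** The first and confirming assessments are at least 4 weeks apart. If confirmation waits for the next scheduled scan, the gap is 18 − 9 = 9 weeks or 30 − 18 = 12 weeks.

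**The case against.** The strongest reply is that the harmful reading is the less natural one. The general rule applies only when there is neither progression nor death, and the fallback then supplies a date for patients who have no last assessment to censor at. The duration-of-response paragraph runs in the same order: death named as an event, conditional censoring, then a plus-1-day fallback that begins "If no tumor assessments were performed after the date of the first occurrence of a complete or partial response". Section 9 also calls patients who leave after any study treatment treatment failures. This makes the intent probable, and it stands to that extent. It does not settle the rule. The duration-of-response fallback has no written exception for death either, the treatment-failure sentence is not tied to PFS, and no other section repairs the PFS text.

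A second reply concerns scope. Of patients who deteriorate, Section 4.3.4 says: "Every effort should be made to document objective progression (i.e., radiographic confirmation) even after discontinuation of treatment". Some early decliners will therefore have a scan and fall outside the fallback. That is right: k counts only deaths with no post-baseline scan.

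A third reply concerns weight. Every week-18 shift above is below one standard error, PFS has no target or decision rule, and the sizes rest on assumed counts. This is also right. The shift is systematic, though, and it costs almost nothing to remove.

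A reader might infer more about irPD, but the documents do not support it:

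- **That an unconfirmed irPD increase has no rule.** Appendix 4 makes confirmation part of irPD and assigns irSD when no other category is met. An unconfirmed increase is therefore irSD, and a living patient is censored at the last assessment.
- **That scanning ends at a progression of unknown type.** The Synopsis and Section 4.4 use RECIST v1.1 for disease progression when they discuss treatment. That indicates the working meaning.
- **That the irPD date could decide the stage-1 gate.** This needs a first increase at week 18, no confirming scan until week 30, dating at the second scan, and no other qualifying patient among the first 10. It is too remote to carry weight.

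**Conclusion.** The point holds as an internal inconsistency in Section 8, with a stated rule that gives a wrong PFS result if followed. The inflation is 40/(40 − k) from week 9 on, or 1.03 to 1.18 for an assumed k of 1 to 6, ignoring other early censoring. An assumed week-18 PFS of 40% would be reported as 41.0% to 47.1%. On the benign reading the bias is zero.

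A reader might conclude that the plan has chosen to exclude early deaths, or that the trial's main result is at risk. Neither follows. The benign reading is the likelier intent. Section 8 counts patients with no post-baseline assessment as non-responders, so the objective response rate is unaffected, and OS counts every death. The harm is confined to PFS and the analyses that use it.

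The missing date for a confirmed irPD is a gap in detail and needs only a clarification.

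**What to change.** In Section 8, before any analysis:

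1. Define PFS as the time from first dose to first progression by the stated criterion (RECIST v1.1 or irRC, each analysed separately) or death from any cause, whichever comes first.
2. Limit the plus-1-day censoring to patients who have no post-baseline tumor assessment and are not known to have died.

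As a minor clarification in Appendix 4, add one sentence saying whether a confirmed irPD is dated at first documentation or at the confirming scan. Appendix 3 back-dates to the earlier scan for equivocal RECIST findings, which is one precedent to consider.

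The cost is two sentences in Section 8 and one in Appendix 4. Sample size, visits and the response-rate decision rule do not change. The only downside is that reported PFS may be slightly less favourable than under the rule as written.

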9. STATISTICAL CONSIDERATIONS

This trial is designed to determine the objective response rate (ORR) using RECIST v1.1 and irRC to nivolumab and ipilimumab when administered in combination to patients with advanced NSCLC and primary resistance to PD-1 axis inhibitor therapy. Details on the response criteria and its duration are described in Section 8 of this protocol. For our primary endpoint we will employ a Simon two-stage design. This design is based on our intuition for a very low response rate and not on any specific experimental evidence. The study design will terminate early if there are no responses or prolonged stability (≥ 24 weeks) using irRC among the first 10 patients enrolled. Otherwise we will enroll a maximum of 40 and reject the null hypothesis if we observe 4 or more

positive responses. For a null hypothesis with a 5% ORR and alternative with a 19% ORR, this criterion has significance level 0.1 and power greater than 85%. The null and alternative hypothesis rates are not motivated by experimental evidence but rather, are examples of one pair of hypotheses that can be tested using this design.

An operating characteristic of this design with other ORRs is plotted here:

We anticipate enrollment at a rate of at least 2 patients per month. Patients who drop out or leave the study before receiving any experimental treatment will be replaced. Patients who leave the study after receiving any study treatment will be considered as treatment failures and not be replaced.

Our secondary analyses correlate ORR, time-to-event measures and correlative metrics listed in Section 7. Specifically, duration of response, progression-free survival (PFS) and overall survival (OS) will be estimated along with the corresponding 95% CI, plotted using the Kaplan-Meier method. These plots will also be prepared separately by RECIST v 1.1 criteria and irRC and tested using the log-rank test. Duration of response, OS, and PFS are defined in Section 8.

Marker data and other metrics listed in Section 7 will be correlated to ORR and PFS using Cox proportional hazard regression methods. These values will be analyzed marginally using heatmaps and single linkage to identify any subpopulations.

The following analysis sets will be defined in this trial:

- Full Analysis Set: All subjects who receive at least 1 dose of any trial treatment.
- Completer Analysis Set: All subjects who complete the trial, all scheduled treatments, all biomarker assessments, and all tumor assessments.
- Safety Analysis Set: All subjects who receive at least 1 dose of any trial treatment but subsequently drop out of the study for any reason.
- Correlative Biomarker Set: All subjects who receive at least one dose of any trial treatment and have at least one set of correlative marker data listed in Section 7.

No formal statistical ORR analyses will be conducted on the 10 additional patients with acquired

resistance, though the finding of immune related response in 1 or more patients would be unexpected, and should prompt further study.

Demographics and baseline laboratory results will be summarized by cohort (primary and acquired resistance to anti-PD-1 axis therapy) and by all patients using descriptive statistics.

Safety analysis will be performed in all treated subjects. Descriptive statistics of safety will be presented using National Cancer Institute (NCI) Common Terminology Criteria for Adverse Events (CTCAE) version 4.0 by cohort (primary and acquired resistance to anti-PD-1 axis therapy) and by all patients. All on-study AEs, drug-related AEs, SAEs and drug-related SAEs will be tabulated using worst grade per NCI CTCAE v 4.0 criteria by system organ class and preferred term. On-study lab parameters including hematology, coagulation, chemistry, liver function and renal function will be summarized using worst grade per NCI CTCAE v 4.0 criteria.

References:

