| 
Study Design:
 
This a phase II study employing a Simon two-stage design to evaluate the primary endpoint of ORR by RECIST v1.1 to combination therapy with nivolumab 3 mg/kg administered intravenously (IV) every 2 weeks, with ipilimumab 1 mg/kg administered IV every 6 weeks, in patients with advanced NSCLC and primary resistance to anti-PD-1 axis therapy. If there is at least one response or prolonged stability (≥ 24 weeks) using irRC appreciated in the first 10 patients who initiate trial therapy, a total of 40 patients will be enrolled. An additional 10 patients with acquired resistance to anti-PD-1 axis therapy will be enrolled in an exploratory cohort receiving the same therapy.
 
Tumor biopsies (and blood collection for pharmacodynamic studies) will be performed just prior to initiating trial therapy, and 9 to 10 weeks after receiving first dose of trial therapy.
 |
| 
Main Criteria for Inclusion/Exclusion:
 
Inclusion
 
 - Age ≥ 18 years - Histologically or cytologically documented, locally advanced or metastatic (i.e., Stage IIIB not eligible for definitive chemoradiotherapy, Stage IV, or recurrent) NSCLC (per the American Joint Committee /AJCC staging system) - ECOG performance status of 0 to 2 |

- Anti- PD-1 Axis therapy (anti-PD-1 or anti-PD-L1, e.g. nivolumab, pembrolizumab, atezolizumab, durvalumab, avelumab) must be the most recent systemic anti-tumor treatment received in all patients, with documented progressive disease:
 - a. Patients to be enrolled to the primary cohort (primary resistance) must have had progressive disease or stable disease less than 24 weeks as the best clinical response to anti-PD-1-axis therapy.
 - b. Patients to be enrolled to the exploratory cohort (acquired resistance) must have had stable disease for at least 24 weeks, partial response, or complete response as the best clinical response to anti-PD-1-axis therapy, with subsequent progression of disease.
- Chemotherapy naive and treated patients will be eligible, with no limit on number of prior therapies. Patients with NSCLC known to harbor an ALK rearrangement, or EGFR mutation known to be sensitive to FDA approved tyrosine kinase inhibitors (TKI), are only eligible after experiencing disease progression (during or after treatment) or intolerance to an FDA approved EGFR TKI or ALK TKI, respectively:

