| 
Statistical Methods:
 
For the primary endpoint of objective response rate (ORR) by RECIST v1.1 among patients with primary resistance to anti-PD-1-axis therapy, a Simon two-stage design will be employed. The design is based on our intuition for a very low anticipated response rate and not on any specific experimental evidence. The study will terminate early if there are no responses or prolonged stability (≥ 24 weeks) using irRC among the first 10 patients enrolled. Otherwise we will enroll a maximum of 40 patients with primary resistance and reject the null hypothesis of no objective response if we observe 4 or more positive responses. For a null hypothesis with a 5% ORR and alternative with a 19% ORR, this criterion has significance level 0.1 and power greater than 85%. The null and alternative hypothesis rates are not motivated by experimental evidence but rather, are examples of one pair of hypotheses that can be tested using this design.
 
Progression-free survival will be estimated with derivation of the corresponding 95% CI, plotted using the Kaplan-Meier method. Overall survival will be plotted using the Kaplan-Meier method.
 |

Time-to-event endpoints (PFS, OS) will be analyzed using the Kaplan-Meier plots. We will correlate OSS and PFS with ORR using Cox proportional hazards regression methods. No formal statistical analyses will be conducted on the 10 additional patients with acquired resistance, though the finding of immune related response in 1 or more patients would be unexpected, and should prompt further study.

Funding, Regulatory, and Feasibility Issues:

- Ipilimumab and nivolumab will be supplied by Bristol Myers Squibb Company.
- Bristol Myers Squibb Company will provide additional trial funding, including funding of serial biopsies.
- IND for trial therapy to be held by [name].

Patient Acceptability/Ethics and Consent Issues:

None anticipated

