4. TREATMENT PLAN

4.1. Study Design

This is a phase II study employing a 2-stage design to evaluate the primary endpoint of ORR to combination therapy with nivolumab 3 mg/kg administered intravenously (IV) every 2 weeks with ipilimumab 1 mg/kg administered IV every 6 weeks in patients with advanced NSCLC and primary resistance to anti-PD-1 axis therapy. If there is at least 1 response or prolonged stability (≥ 24 weeks) using irRC appreciated in the first 10 patients who initiate trial therapy, an additional 30 patients will be enrolled to a total of 40 patients. An additional 10 patients with acquired resistance to anti-PD-1 axis therapy will be enrolled in an exploratory cohort receiving the same therapy.

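### The printed 0.1 level and >85% power belong to a response-only stage 1; because the written gate also opens on irRC stability, the level at 5% ORR is 0.102 to 0.138 for a RECIST v1.1 final count when every RECIST responder passes

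*Combined protocol and SAP*

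**What the plan says.** The Study Design part of the synopsis describes a phase II trial "employing a Simon two-stage design to evaluate the primary endpoint of ORR by RECIST v1.1". Its Statistical Methods part introduces the design with "For the primary endpoint of objective response rate (ORR) by RECIST v1.1 among patients with primary resistance", and says the trial will "reject the null hypothesis of no objective response if we observe 4 or more positive responses", out of a maximum of 40. For 5% against 19% ORR, Section 9 and the synopsis both state that "this criterion has significance level 0.1 and power greater than 85" percent.

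Stage 1 is decided on something broader than a RECIST response. Section 9 stops the trial only if there is neither a response nor stability of at least 24 weeks "using irRC among the first 10 patients enrolled". Section 4.1 gives the matching rule for continuing, with the event judged "using irRC appreciated in the first 10 patients who initiate trial therapy". Both parts of the synopsis agree.

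The event counted at the final test is not defined where the test is stated. Sections 1.1 and 1.2 make RECIST v1.1 ORR primary and irRC ORR secondary. However, Section 9 opens with "This trial is designed to determine the objective response rate (ORR) using RECIST v1.1 and irRC", and Section 8 defines objective response "as determined by investigator assessment using RECIST v1.1 and irRC".

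**The concern.** A Simon design takes its error rates from one binary event counted at both stages. Here the stage 1 event includes prolonged stability by irRC, while the primary endpoint is RECIST v1.1 response. Opening the gate more often, with the final cut-off unchanged, can only raise the chance of rejecting, under the null as well as the alternative. The printed level would then be too low for the rule as written. This is the only formal test of the primary hypothesis. The futility stage is affected too, since it would stop a regimen with 5% ORR less often than a response-only gate.

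Three things that decide the size of the effect are left open:

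- the share of patients who pass stage 1 without a RECIST response;
- whether every RECIST responder passes, since the irRC qualifier may govern responses as well as stability;
- which criterion defines the responses in the final count.

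**Working it through.** **Inputs** (Section 9, synopsis, Section 4.1): n1 = 10; N = 40, so 30 in stage 2; reject at 4 or more; p0 = 0.05; p1 = 0.19. Under Section 9, treated patients who leave count as failures and are not replaced, so the denominator stays at 40.

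**Step 1. Reproduce the printed figures.** With the same response at both stages, P(reject) is the sum over x = 1 to 10 of P(X1 = x; 10, p) × P(X2 ≥ 4 − x; 30, p).

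| Stage 1 responders | Contribution at p = 0.05 | Contribution at p = 0.19 |
|---|---|---|
| 1 | 0.3151 × 0.1878 = 0.0592 | 0.2852 × 0.9425 = 0.2688 |
| 2 | 0.0746 × 0.4465 = 0.0333 | 0.3010 × 0.9856 = 0.2967 |
| 3 | 0.0105 × 0.7854 = 0.0082 | 0.1883 × 0.9982 = 0.1880 |
| 4 or more | 0.0010 | 0.1039 |
| **Total (before rounding)** | **0.1018** | **0.8574** |

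These match the printed 0.1 and >85%. The alternatives tried do not match both figures: single stage with 4 of 40 gives 0.138 and 0.960; two stages with 5 of 40 gives 0.039 and 0.815; single stage with 5 of 40 gives 0.048 and 0.900.

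**Step 2. The omitted path.** This is 0 of 10 RECIST responders, gate opened by stability, then at least 4 of 30.

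- At p = 0.05: 0.95^10 = 0.5987, and 0.5987 × 0.0608 = 0.0364.
- At p = 0.19: 0.81^10 = 0.1216, and 0.1216 × 0.8484 = 0.1031.

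If every RECIST responder passes stage 1, this is the most the wider gate can add. The ceilings are 0.1018 + 0.0364 = 0.138 (0.1381 before rounding) and 0.8574 + 0.1031 = 0.9605. They equal the single-stage values for 4 of 40, as they must when the gate always opens.

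**Step 3. Between the limits.** Let q be the share of all patients who pass stage 1 without a RECIST response. The documents give no value, so these are assumptions. P(reject) = step 1 value + [(1 − p)^10 − (1 − p − q)^10] × P(X2 ≥ 4; 30, p). At p = 0.05, early stopping has probability (0.95 − q)^10, and expected N = 10 + 30 × (1 − that probability).

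| q (assumed) | Level at 5% | Power at 19% | Early stop at 5% | Expected N at 5% |
|---|---|---|---|---|
| 0 | 0.102 | 0.857 | 60% | 22.0 |
| 2% | 0.109 | 0.880 | 48% | 25.5 |
| 5% | 0.117 | 0.906 | 35% | 29.5 |
| 10% | 0.126 | 0.933 | 20% | 34.1 |
| limit | 0.138 | 0.960 | 0% | 40 |

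**Step 4. If some RECIST responders fail the gate.** Let s be the share of RECIST responders who pass (also an assumption). P(reject) = sum over x = 0 to 10 of P(X1 = x) × [1 − (1 − s)^x × (1 − q/(1 − p))^(10 − x)] × P(X2 ≥ 4 − x).

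| s | q | Level at 5% | Power at 19% |
|---|---|---|---|
| 0.95 | 0 | 0.099 | 0.843 |
| 0.95 | 1% | 0.103 | 0.857 |
| 0.90 | 0 | 0.096 | 0.827 |
| 0.90 | 2% | 0.104 | 0.856 |
| 0.90 | 5% | 0.113 | 0.889 |

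With q = 0, power drops below 0.85 once s is below 0.973. The 0.138 ceiling holds for any s and q, provided the final count is RECIST.

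**Step 5. If irRC-only responders were also counted among the 4.** Suppose they add one percentage point (assumption), so the counted event has rate 0.06 when RECIST ORR is 5%. The chance of rejecting is 0.162 if that same event gates stage 1, and 0.217 if stage 2 always opens.

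**The case against.** The strongest reply is that nothing printed is miscalculated. The figures are right, to the precision given, for a response-only Simon rule. If every RECIST responder passes, power stays above 85% throughout, so only the level moves, by at most 0.036. Since q is unknown, this is a bound and not an estimate. The plan also says its 5% and 19% rates are illustrative. A gate that credits stability is a legitimate choice: the four statements of it agree, and the eligibility criteria already use stability of 24 weeks to separate primary from acquired resistance. All of this stands. It limits the weight of the point, but it does not make the printed level that of the written rule.

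Two further replies reduce the side scenarios. A uniform 30% fall in diameter is a 51% fall in the product (0.7 × 0.7 = 0.49), so PR in Appendix 3 and irPR in Appendix 4 nearly coincide. A RECIST responder who misses irPR without irPD is irSD, and passes if that lasts 24 weeks. Low s together with q = 0 is therefore an unlikely pairing, and in step 4 a q of 1% to 2% brings power back above 85%. Similarly, listing irRC ORR as a secondary endpoint favours a RECIST final count, so step 5 shows only the cost of leaving the term undefined. The range in the verdict depends on neither scenario.

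**Conclusion.** The concern holds. The printed level and power are those of a response-only stage 1, and the plan writes a wider one. For a RECIST v1.1 final count with every RECIST responder passing stage 1, the type I error at 5% ORR is between 0.102 and 0.138, and power at 19% is between 0.857 and 0.960. The upper limit is reached only if the gate nearly always opens and should not be read as the expected value. Under these two conditions the power statement remains true and the level is understated by a modest amount. The clearer practical change is in futility: at an assumed q of 5%, the chance of stopping early at 5% ORR is 35% instead of 60%. If a RECIST responder can fail the gate, power above 85% is no longer assured. This should be corrected, but it does not invalidate the design.

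**What to change.** Keep the gate and the cut-off of 4 in 40, and make three changes of wording.

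1. In Section 9 and the synopsis, define the responses counted at the final test as confirmed RECIST v1.1 complete or partial responses. Section 8 already requires confirmation.
2. In Section 9, Section 4.1 and both synopsis parts, state that a RECIST v1.1 response always passes stage 1.
3. In Section 9 and the synopsis, replace the printed level and power with: *Because stage 1 may also be passed on irRC response or prolonged stability, the type I error at 5% ORR is between 0.102 and 0.138 and power at 19% ORR is between 0.857 and 0.960.*

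Section 9 also refers to an operating-characteristic plot, which was not available for this check. It should be compared with the restated figures.

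The cost is text only, with no extra patients and no new cut-off. The stated level becomes slightly less favourable. If a gate judged by irRC alone was intended, the second change settles the rule as well as its wording.
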